7 DATA

7.1 Authorship eligibility guidelines and any intended use of professional writers

Publication

Data from the RCS will be published independently by NEAT ID. All contributing PI investigators will have the opportunity to participate in publication (abstracts and manuscripts) on the analyses.

This study will be conducted in accordance with the guidelines of Good Pharmacoepidemiology Practice (GPP) and Heads of Medicines Agencies (HMA) including archiving of essential documents.

7.2 Data Protection

Personal Data means any information relating to an identified or identifiable natural person (Data Participant), including without limitation pseudonymised information, as defined in the Applicable Law. The *Applicable Law* includes the Regulation (EU) 2016/679, its UK counterpart (UK GDPR) and other relevant regulations. Personal Data will only be collected in line with the study objectives as described in this protocol, and to safeguard participants' rights, only relevant, adequate, limited and necessary data will be collected and used. It is the Data Controller's (the sponsor) responsibility to ensure compliance with the Applicable Law of a data processor (a CRO or an investigator site).

Data processor(s) to aid the Controller with the Applicable Law compliance, must ensure that persons authorised to process the data, have committed themselves to confidentiality or are under an appropriate statutory obligation of confidentiality. Transfer of data must be strictly necessary for the implementation of the research or the use of the results. Transfers of data to a third country will be carried out in line with the applicable law and/or provisions ensuring adequacy (e.g. Standard Contractual Clauses for the transfer of personal data).

Data participant rights are upheld according to the applicable law. If a consent has been given, that consent may be withdrawn at any time. The withdrawal will not affect the lawfulness of the processing carried out prior. The personal data may continue to be processed where there is an appropriate legal basis for such processing. Rights to access, change or move of the collected information are limited as the information must be managed in specific ways for the research to be reliable and accurate.

7.3 Data Retention

Patient data may be retained for up to two (2) years after the last publication of the results of research or, in the absence of publication, until the signing of the final research report.

The personal data of professionals involved in research cannot be kept beyond a period of fifteen years (or in accordance with the current regulations) after the end of the last research in which they participated.

8 APPENDICES

APPENDIX 1 – Schedule of Procedures

	Day1 (Hospital Admission)	Day7 (+/- 1 day) and Day14 (+/- 2 days) / last observation if discharged or died prior to these time points.	Day 28 or last observation after Day 14 if discharged or died prior to this time point.
Medical History ^a	X		
Pregnancy test	X		
HIV test	X		
Vital Signs ^b	X	X	X
Laboratory Testing ^c	X	X	X
Oxygenation ^d	X	X	X
Clinical Status ^e	X	X	X
Other Treatments for COVID-19 ^f	X	X	X
NEWS SCORE ^g	X	X	X

- a. Focused medical history and also the following information (e.g. demographics including ethnicity, baseline characteristics including DM, CV disease and COPD)
- b. SpO2, body temperature, body weight and height on admission
- c. Includes white blood cell count, creatinine, total bilirubin, ALT, AST at admission Day 7 and day 14 or at discharge if before day 14 , radiographic findings at baseline and as available and SARS-CoV-2 pcr, antigen and/or antibody testing.
- d. Includes oxygen supplementation: room air, low flow O2 (L/min and %), high flow O2 (L/min and %), non- invasive positive pressure ventilation (FiO2 or %), mechanical ventilation (FiO2 or %), ECMO (extracorporeal membrane oxygenation)
- e. The ordinal scale is as: 1. Death, 2. Hospitalised, on invasive mechanical ventilation or ECMO, 3. Hospitalised, on non-invasive ventilation or high flow oxygen devices, 4. Hospitalised, requiring low flow supplemental oxygen, 5. Hospitalised, not requiring supplemental oxygen - requiring ongoing medical care (COVID-19 related or otherwise), 6. Hospitalised, not requiring supplemental oxygen - no longer requires ongoing medical care, 7. Not hospitalised
- f. These include corticosteroids, anticoagulants, azithromycin/other antibiotics, anti-inflammatory agents (e.g. Tocilizumab), investigational agents (eg hydroxychloroquine) and immunotherapies such as convalescent plasma and monoclonal antibodies.
- g. NEWS 2 score is based on Respiration rate (per minute), SpO2 (%) Air or oxygen. Systolic blood pressure (mmHg), Pulse (per minute) Consciousness, Temperature (°C)

~This page is to be left blank~

neatid

The European treatment
network for HIV, hepatitis
and global infectious disease

STATISTICAL ANALYSIS PLAN

Protocol Title:	A MULTI-CENTRE, MULTI-COUNTRY RETROSPECTIVE COHORT STUDY TO EVALUATE THE CLINICAL OUTCOMES IN ADULTS WITH COVID-19 WHO HAVE BEEN TREATED WITH REMDESIVIR
SHORT TITLE/ACRONYM	909REM
SPONSOR NUMBER	NEAT ID 909REM
IRAS	293273
SAP VERSION	1.0
SAP VERSION DATE	07.05.2021

Prepared by Study Analyst:

Name: [name]

Date:

Signature:

DOCUMENT HISTORY

Document version number	Date	Reason for change

TABLE OF CONTENTS

1. ABBREVIATIONS AND DEFINITIONS	3
2. STATISTICAL HYPOTHESIS	4
3. STUDY OBJECTIVES AND ENDPOINTS.....	4
4. STUDY METHODS.....	5
4.1 GENERAL STUDY DESIGN AND PLAN	5
4.2 STUDY VARIABLES.....	6
5. SAMPLE SIZE CALCULATION	7
6. GENERAL CONSIDERATIONS.....	7
6.1 TIMING OF ANALYSES.....	7
6.2 ANALYSIS POPULATIONS	7
7. SUMMARY OF STUDY DATA	7
7.1 SUBJECT DISPOSITION	7
7.2 DEMOGRAPHIC AND BASELINE VARIABLES.....	7
8. EFFICACY ANALYSES.....	8
8.1 PRIMARY EFFICACY ANALYSIS.....	8
8.2 SECONDARY EFFICACY ANALYSES	8
9. OTHER ANALYSES	11
11. REPORTING CONVENTIONS.....	12
12. TECHNICAL DETAILS.....	12
APPENDIX.....	13
TABLE 1: BASELINE CHARACTERISTIC OF PARTICIPANTS AND ACCORDING TO THE DISEASE SEVERITY AT BASELINE.....	13
TABLE 2. PRIMARY AND SECONDARY OUTCOMES	16

1. Abbreviations and Definitions

Acronym	Description
ALT	Alanine Amino Transferase
AST	Aspartate aminotransferase
COPD	Chronic obstructive pulmonary disease
COVID	Coronavirus disease
CV	Cardiovascular
DM	Demographic
ECMO	Extracorporeal membrane oxygenation
e-CRF	Electronic Case Report Form
EMR	Electronic Medical Record
HIV	Human Immunodeficiency virus
ICU	Intensive Clinical Unit
ITU	Intensive Terminal Unit
NEAT ID	The European treatment network for HIV, hepatitis and global infectious diseases
NEWS	National Early Warning Score
NK	Not Known
ORDSC	Ordinal Scale Category
PCR	Polymerase Chain Reaction

2. Statistical hypothesis

There is no formal statistical hypothesis to be tested in these analyses. The study will explore the clinical course and outcome of adults with COVID-19 who have been treated with Remdesivir.

3. Study Objectives and Endpoints

Objectives	Endpoints
Primary	
All-cause mortality at Day 28	
 Occurrence of death (all cause) within 28 days
Secondary 
 a 7-point ordinal clinical status scale on Day 7, 14 and 28 (or at last observation if discharged or died prior to this time point) clinical severity at Day 7, 14, 28 as assessed by the NEWS 2 score $\text{SpO}_2 > 94\%$ on room air on day 7, 14 and 28 duration and type (low versus high flow) of oxygen therapy (days) admitted to ICU (yes versus no) number of days spent on ICU/ITU use of mechanical ventilation/ECMO (extracorporeal membrane oxygenation); start and stop dates duration of hospitalisation timing (from first symptoms and from hospitalisation) and duration of use of Remdesivir re-admission with COVID-19 complications or recurrence within 28 days of discharge and outcome (discharged or deceased) 	
 Disease state on a 7-point scale defined as 1. death, 2. hospitalised, on invasive mechanical ventilation or ECMO, 3. hospitalised, on non-invasive ventilation or high flow oxygen devices, 4. Hospitalised, requiring low flow supplemental oxygen, 5. hospitalised, not requiring supplemental oxygen - requiring ongoing medical care (COVID-19 related or otherwise), 6. hospitalised, not requiring supplemental oxygen - no longer requires ongoing medical care, 7. not hospitalised at Day 7 and 14, and 28 (or at last observation if discharged or died prior to this time point) Occurrence of disease severity at day 7, 14, 28 as assessed by NEWS2 score SpO_2 on room air on day 7, 14, and 28 
 Occurrence of $\text{SpO}_2 > 94\%$ on room air on day 7, 14 and 28 Time to $\text{SpO}_2 > 94\%$ on room air Oxygen therapy over the 28 days 
 Frequency of oxygen therapy overall and by type (low versus high flow oxygen) Duration (days) of oxygen therapy Frequency of ICU admission Number of days spent in ICU/ITU Mechanical ventilation over the 28 days

	
 7.1. Frequency of mechanical ventilation/ECMO 7.2. Time (days) on mechanical ventilation/ECMO 8. Duration (days) of hospitalisation 9. Timing of use of Remdesivir 
 9.1. Time (days) from first symptoms to use of Remdesivir 9.2. Time (days) from hospitalisation to use of Remdesivir 9.3. Duration (days) of use of Remdesivir 10. Re-admission within the 28 days following discharge 
 10.1. Frequency of re-admission with COVID-19 within 28 days of discharge 10.2. Frequency of discharge after re-admission 10.3. Frequency of death after re-admission
--	---------------------------------------------------------------------------------------------------------------------------------------------------------------------------------------------------------------------------------------------------------------------------------------------------------------------------------------------------------------------------------------------------------------------------------------------------------------------------------------------------------------------------------------------------------------------------------------------------------------------------------------------------------------------------------------------------------------------------------------------------------------------------------------------------------------------

4. Study Methods

4.1 General Study Design and Plan

This is a multi-centre, multi-country retrospective cohort study. At least 450 COVID-19 cases from up to 20 participating study sites who meet all eligibility criteria will be included in the analysis.

Deidentified data will be extracted from electronic medical record (EMR) databases, clinical registries, case series or additional sources from participating sites and countries, and then entered into a structured e-CRF system. Addition, each site/country will be surveyed to determine the local standard of care therapy for COVID-19 infection and to determine if standard protocols were/are in place for the use of Remdesivir and if/how the protocols changed over time.

Number of Sites and Subjects Planned

Up to 20 centres with 450 cases of Covid-19 treated with at least one dose of Remdesivir

Target Population

Adults with COVID-19 diagnosed and treated with Remdesivir after Aug 31st 2020.

4.2 Study Variables

All the study variables are summarized in the following table.

	Day1 (Hospital Admission) baseline	Day 7 (+/- 1 day) and Day14 (+/- 2 days) / last observation if discharged or died prior to these time points.	Day 28 or last observation after Day 14 if discharged or died prior to this time point.
Medical History ^a	x		
Pregnancy test	x		
HIV test	x		
Vital Signs ^b	x	x	x
Laboratory Testing ^c	x	x	x
Oxygenation ^d	x	x	x
Clinical Status ^e	x	x	x
Other Treatments for COVID-19 ^f	x	x	x
NEWS SCORE ^g	x	x	x

a. Focused medical history and also the following information (e.g. demographics including ethnicity, baseline characteristics including DM, CV disease and COPD)

b. SpO2, body temperature, body weight and height on admission

c. Includes white blood cell count, creatinine, total bilirubin, ALT, AST at admission Day 7 and day 14 or at discharge if before day 14, radiographic findings at baseline and as available and SARS-CoV-2 PCR, antigen and/or antibody testing.

d. Includes oxygen supplementation: room air, low flow O2 (L/min and %), high flow O2 (L/min and %), non-invasive positive pressure ventilation (FiO2 or %), mechanical ventilation (FiO2 or %), ECMO (extracorporeal membrane oxygenation)

e. The ordinal scale is as: 1. Death, 2. Hospitalised, on invasive mechanical ventilation or ECMO, 3. Hospitalised, on non-invasive ventilation or high flow oxygen devices, 4. Hospitalised, requiring low flow supplemental oxygen, 5. Hospitalised, not requiring supplemental oxygen - requiring ongoing medical care (COVID-19 related or otherwise), 6. Hospitalised, not requiring supplemental oxygen - no longer requires ongoing medical care, 7. Not hospitalised

f. These include corticosteroids, anticoagulants, azithromycin/other antibiotics, anti-inflammatory agents (e.g. Tocilizumab), investigational agents (eg hydroxychloroquine) and immunotherapies such as convalescent plasma and monoclonal antibodies.

g. NEWS 2 score is based on Respiration rate (per minute), SpO2 (%) Air or oxygen. Systolic blood pressure (mmHg), Pulse (per minute) Consciousness, Temperature (°C)

For the purpose of the analyses, partial dates will be extrapolated. For example, all dates saved as NK/FEB/2020 will be recoded as 15/FEB/2020 and those saved NK/NK/2020 will be recoded as 15/JUNE/2020. NK means not known.

5. Sample Size calculation

This is a non-interventional, observational study where no formal samples size calculation is to be performed. It is anticipated that at least 450 adults with COVID-19 and treated with Remdesivir could be recruited across centres from NEAT ID Network.

6. General Considerations

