4 ELIGIBILITY CRITERIA

4.1 Inclusion criteria

Diagnosis and Main Eligibility Criteria - Cases(Part 1)

All Adult participants with COVID-19 confirmed by PCR who meet the following criteria:

1. Hospitalised after August 31st, 2020
2. Received at least one dose of Remdesivir (RDV) at any time during hospitalisation

Diagnosis and Main Eligibility Criteria –Controls (Part 2)

Adult participants with COVID-19 confirmed by PCR who meet the following criteria:

1. Hospitalised after August 31st 2020

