4.2 Exclusion criteria

Exclusion Criteria – Cases (Part 1)

1. Received Remdesivir as part of a clinical trial, compassionate use or expanded access program
2. Received Remdesivir prior to this admission at any other health facility than the research sites and whose health records are available.

Exclusion Criteria – Controls (Part 2)

1. Received Remdesivir at any time during hospitalisation

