5 TRIAL PROCEDURES

Only real-world retrospective data will be used for this study. Deidentified retrospective data will be extracted at each clinical site from source data. No personal identifiable data will be transmitted to NEAT ID. Data will be extracted/transcribed in to the eCRF database with standard formatting from electronic medical record (EMR) databases, clinical registries, case series or additional sources from sites/ countries. The data elements will be extracted/transcribed from source data according to the following schedule. Mechanisms to ensure data quality and integrity will be deployed as per applicable standard operating procedures.

	Day1 (Hospital Admission)	Day7 (+/- 1 day) and Day14 (+/- 2 days) / last observation if discharged or died prior to these time points.	Day 28 or last observation after Day 14 if discharged or died prior to this time point.
Medical History ^a	X		
Pregnancy test	X		
HIV test	X		
Vital Signs ^b	X	X	X
Laboratory Testing ^c	X	X	X
Oxygenation ^d	X	X	X
Clinical Status ^e	X	X	X
Other Treatments for COVID-19 ^f	X	X	X
NEWS SCORE ^g	X	X	X

- a. Focused medical history and also the following information (e.g. demographics including ethnicity, baseline characteristics including DM, CV disease and COPD)
- b. SpO₂, body temperature, body weight and height on admission
- c. Includes white blood cell count, creatinine, total bilirubin, ALT, AST at admission Day 7 and day 14 or at discharge if before day 14, radiographic findings at baseline and as available and SARS-CoV-2 pcr, antigen and/or antibody testing.
- d. Includes oxygen supplementation: room air, low flow O₂ (L/min and %), high flow O₂ (L/min and %), non- invasive

positive pressure ventilation (FiO2 or %), mechanical ventilation (FiO2 or %), ECMO (extracorporeal membrane oxygenation)

- e. The ordinal scale is as: 1. Death, 2. Hospitalised, on invasive mechanical ventilation or ECMO, 3. Hospitalised, on non-invasive ventilation or high flow oxygen devices, 4. Hospitalised, requiring low flow supplemental oxygen, 5. Hospitalised, not requiring supplemental oxygen - requiring ongoing medical care (COVID-19 related or otherwise), 6. Hospitalised, not requiring supplemental oxygen - no longer requires ongoing medical care, 7. Not hospitalised

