8.1 Primary Efficacy Analysis

Primary endpoint	
 Occurrence of death within 28 days
Analysis population	
 Full population analysis
Descriptive statistics and graphical representation	
 Data will be summarized with proportion and 95% confidence interval globally and according to disease severity at baseline (ORDSC score 2 vs 3-4 vs 5) LogRank test will be used to compared the 3 groups P-values will be two-tailed with a significant level at 5%. Kaplan-Meier curves will be plotted
Statistical analysis	
Kaplan-Meier estimates will be used to calculate the proportions and the 95% confidence intervals
 
Time to death will be defined as the time between the date of hospitalization and the date of death or discharge from hospital or last observation
 
Participant with missing clinical status or alive at day 28 will be censored at the date of last observation

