Descriptive statistics and graphical representation	
 • Data will be summarized with proportion or median and 95% confidence interval according to the endpoint • Data will be summarized globally and according to disease severity at baseline (ORDSC score 2 vs 3-4 vs 5) • LogRank test will be used to compared the 3 groups • P-values will be two-tailed with a significant level at 5% • Kaplan-Meier curves will be plotted
Statistical analysis	
Kaplan-Meier estimate will be used to estimate the proportion of subject with oxygen therapy and by type (low versus high flow oxygen), the proportion of subjects admitted in ICU and the proportion of those having received mechanical ventilation or ECMO. Time to event will be defined as the time between the date of first symptom and the date of event of interest. Participants not experienced the event of interest will be censored at last observation date. Participants who deceased before will be considered as having the event.
 
The duration (days) of oxygen therapy, the number of days spent in ICU/ITU and the time (days) on mechanical ventilation/ECMO will be estimated using Kaplan-Meier estimates as well as the associated 95% confidence intervals. The time will be defined as the time between the start date of event and the end date of the event of interest or hospital discharge. Subjects who died will be censored at day 28.

Endpoint	8. Duration (days) of hospitalization
----------	----------------------------------------------

Analysis population	
 Full population analysis
Descriptive statistics and graphical representation	
 Data will be summarized with median and 95% confidence interval globally and according to disease severity at baseline (ORDSC score 2 vs 3-4 vs 5) LogRank test will be used to compared the 3 groups P-values will be two-tailed with a significant level at 5% Kaplan-Meier curves will be plotted
Statistical analysis	
Kaplan-Meier method will be used to calculate the medians and the 95% confidence intervals. Time (days) from hospitalization to hospital discharge will be defined as the time between the date of hospitalization for COVID-19 and the date of hospital discharge. The event will be hospital discharge. Subjects who died will be censored at day 28.

9. Other Analyses

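### Hospital-onset COVID-19 cases are eligible, but Day 1 and the 28-day mortality clock start at admission for everyone, so baseline, Day 7/14 status and part of the mortality window can precede infection

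*SAP*

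**What the plan says.** **Eligibility.** Protocol 4.1 opens the case criteria with "All Adult participants with COVID-19 confirmed by PCR who meet the following criteria" and lists two conditions: "Hospitalised after August 31st, 2020" and "Received at least one dose of Remdesivir (RDV) at any time during hospitalisation". The two case exclusions in Protocol 4.2 concern how or where remdesivir was received; the first is "Received Remdesivir as part of a clinical trial, compassionate use or expanded access program". The target population in Protocol 3 and 6.1 and SAP 4.1 adds no condition on the reason for admission or on the timing of infection.

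**Day 1.** The schedules in Protocol 5 and Appendix 1 set Day 1 at hospital admission. SAP 4.2 does the same and labels it baseline: "Day1 (Hospital Admission) baseline". No other index date is offered. The ordinal score on that day (2 vs 3-4 vs 5) stratifies the baseline table and the outcome analyses in SAP 7.2, 8 and 9.

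**Time origins.** SAP 8.1: "Time to death will be defined as the time between the date of hospitalization and the date of death". SAP 8.2, endpoint 8 (duration of hospitalisation): "the time between the date of hospitalization for COVID-19 and the date of hospital discharge". The SAP 8.2 entries for time to SpO2 above 94% and for occurrence of oxygen therapy, ICU admission and ventilation/ECMO use the date of first symptom.

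**The concern.** The study sets out to describe the clinical course of adults with COVID-19. That needs a clock that starts when COVID-19 is present. A patient admitted for another illness who becomes infected on the ward meets every criterion, yet the clock starts at an admission unrelated to COVID-19.

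Four things follow:

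- The baseline stratum, which divides almost every table, records the severity of another illness.
- Day 7 and Day 14 ordinal and NEWS 2 results may be readings from before infection.
- The 28-day mortality window, the SAP's primary endpoint, includes days on which a death would have kept the patient out of the cohort. Counting them lowers the captured 28-day COVID-19 mortality.
- The remaining origins either do not exist for this patient (duration of hospitalisation, a primary objective in Protocol 2.1) or can fall after the event being timed (the endpoints that run from first symptom).

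This is separate from any delay in treatment. It remains even if remdesivir starts on the day of diagnosis.

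**Working it through.** The plan states no figure to reproduce. The 450 cases are an anticipated number with no formal calculation (Protocol 6.2, SAP 5).

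**1. Which visits precede infection.** Let D be the hospital day of infection, with admission as Day 1. A visit on nominal day v precedes infection if D > v. The days from infection inside the 28-day window are 28 - D + 1 = 29 - D.

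| D | Day 1 before | Day 7 before | Day 14 before | Days from infection in window |
|---|---|---|---|---|
| 3 | yes | no | no | 26 |
| 8 | yes | yes | no | 21 |
| 10 | yes | yes | no | 19 |
| 15 | yes | yes | yes | 14 |

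With the visit windows (Day 7 ± 1, Day 14 ± 2), a visit is certain to precede infection only if D > 8 or D > 16 respectively.

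**2. One patient.** Admitted 1 October for another illness, first symptoms 20 October, remdesivir 22 October, discharged 10 November.

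- Baseline is 1 October, Day 7 is 7 October and Day 14 is 14 October, all before onset of symptoms. Infection itself is not observed and comes somewhat before symptoms.
- Day 28 is 28 October, 8 days after onset.
- Endpoint 8 has no start date, because there was no hospitalisation for COVID-19. From admission the stay would be 40 days; from first symptom it would be 21 (40 - 19).
- If SpO2 was above 94% on room air on 7 October, that event lies 13 days before its own origin (20 October). The same holds for an ICU stay that began before onset. Kaplan-Meier cannot use a negative time, and the SAP gives no rule for it.

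**3. Illustration of size.** None of these inputs is in the documents: hospital-onset share f = 5%, 10%, 20% (about 22, 45, 90 of 450); D = 5, 10, 15; 28-day mortality from infection 12% with constant hazard.

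Captured mortality in these patients = 1 - 0.88^((29 - D)/28):

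- D = 5: 1 - 0.88^(24/28) = 10.4%
- D = 10: 1 - 0.88^(19/28) = 8.3%
- D = 15: 1 - 0.88^(14/28) = 6.2%

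Overall = (1 - f) × 12% + f × captured value:

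- smallest effect (f = 5%, D = 5): 0.95 × 12% + 0.05 × 10.4% = 11.9%
- largest effect (f = 20%, D = 15): 0.80 × 12% + 0.20 × 6.2% = 10.8%

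**4. Stay, only if admission is used by default.** Each such patient adds D - 1 = 4, 9 or 14 days. With an assumed lognormal COVID-19 stay (median 9 days, log-SD 0.7), the overall median moves from 9.0 to about 9.2-9.4 at 5%, 9.5-9.9 at 10% and 9.9-11.3 at 20%.

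**The case against.** **The effect may be small.** This stands as a statement about overall figures. With 450 patients and 12% mortality, the sampling half-width is 1.96 × √(0.12 × 0.88/450) = 3.0 percentage points, against an illustrative shift of 0.1 to 1.2 points. For the median stay, the half-width under the lognormal above is about 1.96 × 9 × 0.7 × √(2π)/(2√450) = 0.7 days. The 5% scenarios fall inside that and most of the larger ones outside. But this error does not shrink with more patients, and it would be larger in any stratum where these patients collect.

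**The stay endpoint is already tied to COVID-19.** Correct. A reader might infer that duration of hospitalisation counts non-COVID days for these patients. Endpoint 8 does not say that. Its start date is undefined for them, and earlier days enter only if the admission date is substituted.

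**SpO2, oxygen, ICU and ventilation do not run from admission.** Also correct. Their difficulty is events before the origin, not the wrong origin.

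**The dates to identify these patients are already needed.** Endpoints 9.1 and 9.2 (SAP 9) use first symptom, admission and remdesivir start. That makes the repair cheap, but nothing in the SAP uses those dates to separate hospital-onset cases.

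**Conclusion.** The concern holds for the baseline stratum, for Day 7 and Day 14 ordinal and NEWS 2 results, and for the primary mortality endpoint. There the written rules, applied as they stand, give the wrong result for hospital-onset cases. For duration of hospitalisation and the endpoints timed from first symptom, the defect is a missing rule.

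The size cannot be derived from the documents, because they give no hospital-onset share. The figures above show direction and order of magnitude under stated assumptions. The mortality direction is firm: time that must be survived before infection can only reduce the deaths from COVID-19 captured by Day 28.

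A reader might also infer that these patients gather in the mild stratum (score 5) and lengthen its stay. The documents do not support that. Score 5 does allow for care unrelated to COVID-19, but a patient admitted to intensive care and ventilated for another illness would score 2, and one on low-flow oxygen for another lung disease would score 4. The direction of stratum misplacement is unknown.

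**What to change.** Amend SAP 4.2, 7.1, 8.1 and 8.2, and align Protocol 5:

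1. State that hospital-onset cases are included, and flag them: first symptom (or first positive PCR, if there were no symptoms and the date is available) later than admission by more than a pre-stated minimum gap. The gap keeps out patients who were incubating at admission or screened positive on day 2. Do not flag on an imputed date alone: SAP 4.2 recodes an unknown day to the 15th, so a patient admitted on 5 October with symptoms on an unknown day in October would look 10 days hospital-onset.
2. Report their number in SAP 7.1.
3. Give Day-28 mortality, Day 7 and Day 14 ordinal and NEWS 2 results, and duration of hospitalisation with and without them.
4. Where they are included, use one COVID-19 index date, the later of admission and first symptom or positive PCR, as the origin for 28-day death (8.1) and for stay (endpoint 8). State in SAP 4.2 that their Day 1, 7 and 14 values are admission-based.
5. State how an event before first symptom is handled in the endpoints timed from that date.
6. Leave endpoint 9.2 timed from admission, as its name says.

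**Cost.** A few extra analyses, and possibly a PCR date for the asymptomatic minority; the documents list PCR testing but no date of first positive result. Visits need no re-abstraction for the with/without comparison. The index-date analysis needs death and discharge dates to 28 days after the index. In the example that is 16 November, 19 days beyond the last scheduled time point. Where those dates are missing, the patient is censored at last observation.

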6.2 Analysis Populations

All enrolled participants who met the eligibility criteria and with data available at baseline will be included in the Full Analysis Population. The primary endpoint and all secondary endpoints will be analysed on this Full Analysis population.

7. Summary of Study Data

All continuous variables will be summarized using the following descriptive statistics: n (non-missing sample size), mean, standard deviation, 1st quartile, median, 3rd quartile, maximum and minimum. The frequency and percentages (based on the non-missing sample size) of observed levels will be reported for all categorical variables.

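### SAP 4.2 recodes year-only 2020 dates to 15 June 2020, which is 78 to 199 days before any eligible 2020 admission, and sets no limit on imputed dates from the patient's known dates.

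*SAP*

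**What the plan says.** SAP 4.2 (Study Variables) announces that partial dates will be filled in for analysis and illustrates how: "all dates saved as NK/FEB/2020 will be recoded as 15/FEB/2020 and those saved NK/NK/2020 will be recoded as 15/JUNE/2020". No type of date is exempted. Neither document requires an imputed date to agree with the patient's admission, discharge, death or last observation.

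The study window is explicit. Protocol 4.1 requires cases to be "Hospitalised after August 31st, 2020" and to have "Received at least one dose of Remdesivir (RDV) at any time during hospitalisation". SAP 4.1 gives the target population as "Adults with COVID-19 diagnosed and treated with Remdesivir after Aug 31st 2020".

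Most endpoints are differences between dates:

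- Time to death (SAP 8.1) is "the time between the date of hospitalization and the date of death or discharge from hospital or last observation".
- Oxygen, ICU and ventilation durations (SAP 8.2) are "the time between the start date of event and the end date of the event of interest or hospital discharge".
- Length of stay (SAP 8.2) is "the time between the date of hospitalization for COVID-19 and the date of hospital discharge".
- Remdesivir duration (SAP 9) runs from start to stop.
- Time to SpO2 above 94%, times to oxygen, ICU and ventilation (SAP 8.2) and one of the remdesivir timing endpoints (SAP 9) start at first symptom.

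**The concern.** The year-only rule gives in-hospital events a date on which no eligible patient could have had them. If the admission or other start date is known and the end date is year-only 2020, the interval is negative. The SAP does not say whether such a record is dropped, set to zero or queried, so the analyst would have to decide with the data in hand.

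The unknown-day rule causes quieter trouble. It can put an event before admission, or carry a death from inside the 28-day window to outside it. The second case produces no impossible value, so a range check on the times would not show it, and it touches the primary endpoint.

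A year-only symptom onset does not give an impossible value either. It does make every interval measured from onset very long.

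**Working it through.** The SAP reports no calculation here, so there is no figure of its own to reproduce. The check is calendar subtraction.

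**Inputs.** The recoding rules come from SAP 4.2. The earliest eligible admission is 1 September 2020 (Protocol 4.1) and the last 2020 admission date is 31 December 2020. September to December contain 30 + 31 + 30 + 31 = 122 possible admission dates. No distribution of admissions or deaths is assumed, and no 2021 date is recoded.

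**1. Year-only 2020 date of an in-hospital event, admission known.** Imputed time = 15 June 2020 − admission date.

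- Admission 1 September: −(15 + 31 + 31 + 1) = −78 days.
- Admission 31 December: −(78 + 121) = −199 days.
- All 122 admission dates give a negative time.

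**2. Year-only 2020 symptom onset, 2020 admission.** Any event on or after admission is at least 78 days from 15 June, so each first-symptom clock is at least 78 days.

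**3. Unknown day, event in the month of admission.** Imputed time = 15 − d, where d is the day of the month of admission. It is negative for d of 16 or more.

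- Events on or after the admission day: 15 + 16 + 15 + 16 = 62 of 122 dates, with times from −1 (d = 16) to −16 (d = 31).
- Events strictly after the admission day: the last day of each month drops out, leaving 14 + 15 + 14 + 15 = 58 dates and times from −1 to −15.

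**4. Unknown day, death in the month after admission, both in 2020.** The admission dates are 1 September to 30 November, 30 + 31 + 30 = 91 dates. A death within 28 elapsed days can be moved out if the 1st of the next month is at most 28 days after admission and the 15th is more than 28 days after it.

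| Admission month | 1st of next month | 15th of next month | Affected d | Imputed time |
|---|---|---|---|---|
| September | 31 − d ≤ 28 | 45 − d > 28 | 3 to 16 | 29 to 42 days |
| October | 32 − d ≤ 28 | 46 − d > 28 | 4 to 17 | 29 to 42 days |
| November | 31 − d ≤ 28 | 45 − d > 28 | 3 to 16 | 29 to 42 days |

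That is 14 + 14 + 14 = 42 of 91 dates.

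**Sensitivity to the day count.** The schedule in SAP 4.2 calls admission Day 1, so Day 28 could mean admission + 27. Replacing 28 by 27 moves each window one day later (4–17 September, 5–18 October, 4–17 November). The count stays at 42 of 91.

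**Illustration (hypothetical patient).** Admission on 10 October, death recorded with unknown day in November, Day 28 status recorded as death. The rule gives 15 November, 36 days after admission. Counting elapsed days, the recorded status limits the death to 1–7 November, 22 to 28 days after admission.

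**The case against.** The recodings are introduced as examples, and the February 2020 one could not itself be an eligible in-hospital date. It may therefore be a generic illustration of format and not a rule devised for discharge or death dates. Protocol 5 also promises data-quality mechanisms. This does not cure the problem. The wording covers all dates, no other rule appears in either document, and the data-quality sentence sets no limit on dates imputed at analysis.

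Partial dates may be rare. That stands: their number is not given, and the effect on the results may be small or nil.

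A reader might go further than the documents allow in four ways.

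- **That a displaced death is certainly lost.** Clinical status, with death as a category, is collected at Day 28 or at last observation, and SAP Table 2 lists the number of deaths by Day 28 separately from the Kaplan-Meier estimate. The SAP does not say whether recorded status or imputed date prevails, so the death may be missed by the estimate, and no more can be said.
- **That about half of patients are affected.** 62 of 122 and 42 of 91 count calendar dates, not patients.
- **That a year-only admission date belongs to the same fault.** SAP 6.2 admits "All enrolled participants who met the eligibility criteria and with data available at baseline will be included in the Full Analysis Population", so such a date is mainly an eligibility question and is not counted here.
- **That an onset date before 1 September 2020, or after admission, is an error in itself.** Eligibility excludes neither. The onset-to-treatment covariate in Protocol 6.3, split at 7 days, is affected only if that model uses dates imputed under SAP 4.2.

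**Conclusion.** The concern holds. Applied as written to a year-only 2020 in-hospital date, SAP 4.2 gives a result that contradicts the study's own eligibility window by 78 to 199 days. With a known start date the interval is negative, and no handling is specified. Year-only 2020 onset adds an artificial 78 days or more to the first-symptom clocks of 2020 admissions.

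The unknown-day rule is incomplete. It can date same-month events 1 to 16 days before admission (1 to 15 if strictly after the admission day). It can also date a next-month death within 28 elapsed days to 29 to 42 days after admission.

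The size of these displacements rests only on the calendar and the eligibility date. It does not extend to the mortality estimate, for which no effect is claimed. The rule should be corrected before the analysis because it gives impossible values and is cheap to repair.

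**What to change.** Add a short paragraph to SAP 4.2:

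- An imputed date must lie within the known month or year and within the interval set by the patient's known dates. In-hospital dates lie between admission and discharge, death or last observation. Remdesivir stop is on or after start. Readmission is on or after discharge. A death date must agree with the recorded Day 7, 14 and 28 clinical status.
- Use the 15th or 15 June only if it falls in that interval, and otherwise the interval midpoint. For the patient illustrated above, the midpoint of 1–7 November is 4 November, 25 days after admission.
- Treat year-only symptom onset as missing for intervals that start at onset. Keep those participants in every admission-based analysis, including mortality.
- Flag imputed dates and report how many there are.
- Run one sensitivity analysis of 28-day mortality with imputed dates at their earliest and latest feasible values.

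The cost is a little programming and a few participants missing from the onset-based intervals. Site queries for partial admission, discharge and death dates would help but are optional; their number depends on the unknown count of partial dates.
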